## 4.2. Participant Dispositions

Reasons for discontinuation prior to randomization including screen failure will be summarized for all participants who sign the informed consent form.

The number and percentage of participants who have completed/discontinued from the study/treatment will be summarized by treatment using the Randomized Population. The individual reasons for discontinuation will also be included in the summary. Comparison will be conducted using the Fisher's exact test.

A listing of the reasons for study/treatment discontinuations will be generated for the Randomized Population. A listing of the randomized treatment for this study will also be provided.

Time to permanent discontinuation of study treatment, time to study discontinuation and time to early discontinuation of study treatment due to AEs (if there is a sufficient number to warrant a summary) will be presented as a figure.

# 4.3. Primary Endpoint Analysis

#### 4.3.1. **Definition of Endpoint(s)**

The primary endpoint of this study is the HbA1c change from baseline to Week 52 (Visit 33). The HbA1c is reported in unit of % by central laboratory and will be converted to the unit of mmol/mol using the following formula: HbA1c in mmol/mol = 10.93 \* HbA1c in % - 23.5 (NGSP 2010). The HbA1c analysis will be conducted for both units.

#### 4.3.2. Main Analytical Approach

The primary objective is to test the hypothesis that LY3209590 is noninferior to insulin glargine on glycemic control in the targeted study population. The noninferiority test will be based on

either of the 2 estimands: *treatment regimen estimand* for the US FDA submission and *efficacy estimand* for registrations in other countries. The full significance level of 0.05 will be used for each estimand.

This table provides the details of treatment regimen estimand and efficacy estimand.

	Treatment Regimen Estimand	Efficacy Estimand
Analysis Population	All participants in EAS1 with non-missing baseline measure	All participants in EAS2 with non- missing baseline measure and at least one non-missing postbaseline scheduled measure
Analysis Data	All non-missing observations at baseline and Week 52 (Visit 33) regardless of the use of study intervention or rescue medications.	All non-missing observations at baseline and all scheduled postbaseline timepoints during treatment period (that is, Weeks 2, 4, 8, 12, 16, 26, 36, and 52) prior to the date of last study dose + 10 days for LY3209590 (+1 day for Glargine), or the initiation of rescue medication, whichever is earlier for participants with intercurrent events.
Missing Data	There may be missing values at Week 52 (Visit 33) due to early study discontinuation. The missing values will be imputed using multiple imputation by the retrieved dropout approach. The retrieved dropout participants are those who discontinue study intervention prior to Week 52 but have non-missing measures at Week 52 in the same treatment arm. If there are only a limited number of retrieved participants that leads to a failure in performing the multiple imputation analysis, such as the model cannot converge, or the number of retrieved dropout participants is small (i.e., at least 1 arm has < 8 participants who discontinued study treatment early and have endpoint visit measurements), the missing HbA1c at Week 52 will be imputed by return-to-baseline multiple imputation approach (Qu and Dai, 2022).	There may be missing values due to the early discontinuation of study intervention or use of rescue medication. The MMRM model will be used, and the missing values will be handled in the MMRM analysis under the assumption of missing at random.

	Treatment Regimen Estimand	Efficacy Estimand
Analysis Model	After the imputation, the observed	The MMRM model will include
	and imputed data will be analyzed by	treatment, strata (country and GLP-1 RA
	the ANCOVA model using	treatment at randomization), visit and
	treatment, strata (country and GLP-1	treatment-by-visit interaction as fixed
	RA treatment at randomization), and	effects, and baseline of the dependent
	baseline value of the dependent	variable as a covariate. The Kenward-
	variable as independent variables.	Roger approximation will be used to
	The statistical inference will be based	estimate denominator degrees of freedom
	on the multiple imputation	for the MMRM models. An unstructured
	framework by Rubin (1987).	covariance structure will be used to
		model the within-participant errors. If this
		structure fails to converge, the following
		covariance structures will be used in
		order until one converges:
		1. Toeplitz with heterogeneity
		2. autoregressive with
		heterogeneity
		3. compound symmetry with
		heterogeneous variances
		4. Toeplitz
		5. Autoregressive
		6. compound symmetry without
		heterogeneous variances.

Abbreviations: ANCOVA = analysis of covariance; EAS1 = efficacy analysis set 1; EAS2 = efficacy analysis set 2; GLP-1 RA = glucagon-like peptide-1 receptor agonist; HbA1c = hemoglobin A1c; MMRM = mixed model repeated measurement.

The 2-sided 95% CI of the LS mean difference (LY3209590 – insulin glargine) in the HbA1c change from baseline to Week 52 (Visit 33) will be estimated. For both estimands, LY3209590 will be declared noninferior to insulin glargine if the upper limit of the 2-side 95% CI for the LS mean difference in the HbA1c (measured in %) change from baseline is below NIM of +0.4%. In addition, the 95% CI for the LS mean difference will be compared to an alternative NIM of +0.3%.

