# Missing measures

Missing measures at the primary endpoint will be imputed using multiple imputation by the retrieved dropout approach. The retrieved dropout participants are those who discontinue study intervention prior to Week 52 (Visit 33) but have non-missing measures at Week 52 (Visit 33).

If there are only a limited number of retrieved participants that leads to a failure in performing the multiple imputation analysis, such as the model cannot converge, or the number of retrieved dropout participants is small, the missing HbA1c at Week 52 (Visit 33) will be imputed by return-to-baseline multiple imputations.

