## Local laboratory testing option

Local laboratory testing may be conducted in lieu of central laboratory testing, except for HbA1c and serum glucose testing. Lilly-designated laboratory testing must be retained for HbA1c and serum glucose.

The local laboratory must be qualified in accordance with applicable local regulations.

Obtain local labs for safety hematology, chemistry, hormone panel, and urinalysis, when applicable, per the SoA. Safety labs should be obtained as specified in the SoA.

All labs will be reviewed by the investigators. Sign and date review of local labs per normal process and follow-up with the participant as needed. Results will not be recorded in the CRF.

Lilly Medical should be informed of any labs that meet criteria for temporary or permanent study intervention discontinuation.

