# 2. Statistical Hypotheses

#### **Primary Hypothesis**

The primary objective of this study is to test the hypothesis that LY3209590 is not inferior to insulin glargine on glycemic control as measured by change in HbA1c from baseline to Week 52 (Visit 33) in participants with T2D who are starting basal insulin for the first time.

The null hypothesis ( $H_0$ ) is the difference between LY3209590 versus insulin glargine in the change from baseline to Week 52 (Visit 33) in HbA1c is greater than the non-inferiority margin (NIM).

The NIMs of 0.4% and 0.3% will both be tested to meet regulatory requirements. The 2-sided 95% CI will be used for testing the noninferiority.

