## 5. Sample Size Determination

Approximately 670 participants will be randomly assigned to LY3209590 and insulin glargine in a 1:1 ratio.

With the assumption of 15% dropout at Week 52 (Visit 33), approximately 284 participants on LY3209590 and 284 participants on insulin glargine will complete 52 weeks of treatment.

The number of completers will provide at least 99% statistical power to show noninferiority between LY3209590 and insulin glargine using the upper limit of a 2-sided 95% CI and these assumptions:

- NIM of 0.4%
- no true difference between treatment groups, and
- an SD of 1.1%.

This sample size has at least 90% statistical power to show noninferiority between LY3209590 and insulin glargine using a 0.3% NIM at Week 52 (Visit 33).

The number of completers will provide 90% statistical power to show superiority between LY3209590 and insulin glargine for change in HbA1c from baseline to Week 52 (Visit 33), assuming an SD of 1.1% and true mean difference of -0.3%, and alpha of 0.05.

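### The treatment regimen analysis has one imputation rule for missing Week 52 HbA1c and none for participants still on study treatment, which can bias the comparison

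*SAP*

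**What the plan says.** Protocol 9.3.2 (Missing measures) is unqualified: "Missing measures at the primary endpoint will be imputed using multiple imputation by the retrieved dropout approach". The table of baseline and postbaseline observations in SAP 4.1 likewise applies multiple imputation to missing HbA1c at Visits 33 and 25 without reference to treatment status. A same-day unplanned measurement may stand in for a missing planned one.

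SAP 4.3.2 first names early study discontinuation as the source of missing Week 52 values, then states "The missing values will be imputed using multiple imputation by the retrieved dropout approach". Donors are participants in the same arm who stopped study intervention but have a Week 52 value. If the model fails, or if at least one arm has fewer than 8 donors, return-to-baseline multiple imputation is used instead.

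The rule carries over to Week 26 HbA1c and SMBG fasting glucose (SAP 4.4.2.1) and to the HbA1c responder endpoints and fasting serum glucose (SAP 4.5.1). No section gives a rule for a value missing while the participant is still on study treatment.

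**The concern.** The treatment regimen estimand (Protocol 3, SAP 1.1) concerns the outcome under whatever treatment course followed randomisation. For a participant still taking study insulin at Week 52, that course is continued treatment, so the natural reference is same-arm participants who are also still on treatment. The stated rule draws instead from people who stopped, or centres the value on baseline.

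Three things are at stake:
- If on-treatment missingness or the gap differs by arm, the treatment difference shifts.
- Under the fallback, a true difference is pulled toward zero even with equal missingness, and in a noninferiority test that is the anti-conservative direction.
- Drawing more values from a small donor pool adds noise.

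**Working it through.** **The plan's own figures.** From SAP 5: 670/2 = 335 per arm; 15% dropout leaves 335 × 0.85 = 284.75, taken as 284; SD 1.1; "no true difference between treatment groups". From SAP 2: "The 2-sided 95% CI will be used for testing the noninferiority". So SE = 1.1 × √(2/284) = 0.0923 and power = Φ(margin/SE − 1.96).

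- Margin 0.4: Φ(4.33 − 1.96) = 99.1%. The SAP says "The number of completers will provide at least 99% statistical power to show noninferiority".
- Margin 0.3: Φ(3.25 − 1.96) = 90.1%. The SAP says "This sample size has at least 90% statistical power to show noninferiority between LY3209590 and insulin glargine using a 0.3% NIM".
- Superiority at −0.3: the same arithmetic gives 90.1%.

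All three reproduce. They are stated for completers, so the imputation rule does not change them.

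**Assumed inputs (not in the documents).** m = share of an arm on treatment with a missing Week 52 value, 1% to 5%. g = imputed mean minus on-treatment mean change, 0.5 to 1.5 HbA1c points.

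**Step 1: retrieved-dropout imputation.** Bias in the difference = m_LY × g_LY − m_G × g_G.

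- Equal m and equal g: 0.
- 3% vs 1%: 0.02 × 0.5 = 0.01 up to 0.02 × 1.5 = 0.03.
- 5% vs 2%: 0.03 × 0.5 = 0.015 up to 0.03 × 1.5 = 0.045.
- Extreme corner, with both inputs unequal: 0.05 × 1.5 − 0.01 × 0.5 = 0.07.

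With equal gaps, the arm with more missing samples is disadvantaged. A shift of 0.03 against LY3209590 gives power Φ(0.37/0.0923 − 1.96) = 98.0% at margin 0.4 and Φ(0.27/0.0923 − 1.96) = 83.3% at margin 0.3.

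**Step 2: return-to-baseline fallback, equal m.** The imputed mean change is about zero in both arms, so a true difference D becomes D(1 − m). After imputation all 335 per arm contribute, so SE = 1.1 × √(2/335) = 0.0850. With D at the margin and SE held fixed, one-sided type I error = Φ(mD/SE − 1.96), nominally 2.5%.

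| m per arm | D = 0.4 becomes | Type I error, margin 0.4 | Type I error, margin 0.3 |
|---|---|---|---|
| 1% | 0.396 | 2.8% | 2.7% |
| 2% | 0.392 | 3.1% | 2.9% |
| 5% | 0.380 | 4.2% | 3.7% |

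For superiority the shrinkage is conservative. Power at −0.3 (SE 0.0923) falls from 90.1% to Φ(0.294/0.0923 − 1.96) = 89.0% at 2%, and to 87.0% at 5%.

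**Step 3: simulation of one rule against a split rule.** Settings: 335 per arm, SD 1.1, 10% stop treatment, half of those retrieved (335 × 0.10 × 0.5, about 17 donors per arm, above the fallback trigger), g = 0.7, 20 imputations, 1,500 runs, no baseline covariate. True difference 0; Monte Carlo SE of each mean estimate about 0.0025.

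| On-treatment missing, LY / glargine | Mean estimate, one rule | Mean estimate, split | Power at 0.4, one rule | Power at 0.4, split |
|---|---|---|---|---|
| 5% / 1% | +0.029 | −0.002 | 96.2% | 98.6% |
| 1% / 5% | −0.025 | −0.001 | 99.5% | 99.1% |
| 5% / 5% | +0.004 | +0.002 | 96.5% | 99.3% |

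Step 1 predicts 0.04 × 0.7 = 0.028 for the unequal rows, in line with the simulation. The last row has no bias, but the single rule loses precision.

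**The case against.** **The SAP may simply be silent.** A reader might infer that the plan deliberately treats on-treatment participants as having stopped. SAP 4.3.2 does not say so. It introduces the rule for values missing through early study discontinuation, and there the donor group fits, because Protocol 7.2 ends study intervention when a participant leaves the study. This stands as to intent. It still leaves the on-treatment case with either no rule or, under the unqualified texts in Protocol 9.3.2 and SAP 4.1, an unsuitable one.

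**The local-testing restriction is not evidence of lost samples.** Protocol 10.7 says "Lilly-designated laboratory testing must be retained for HbA1c and serum glucose", from which a reader might infer that remote visits will cost HbA1c values. The same appendix allows mobile healthcare visits and blood draws at other locations, and asks that Week 52 keep to schedule where possible. The restriction is on where samples are tested, so it gives no support for a high missing rate.

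**The size is assumed.** This stands. Nothing in the documents suggests that missed samples would differ by arm. Protocol 7.1 lets participants who stop study insulin take another glucose-lowering medication, so retrieved dropouts may lie closer to on-treatment values than a 0.5-point gap implies.

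**Sensitivity analyses exist.** SAP 4.3.3.1 plans a two-way tipping point analysis, and a rerun that adds 0.4 to every imputed LY3209590 value. For the on-treatment share m, that addition is 0.4m, which equals the fallback's shrinkage of a true difference at the 0.4 margin (0.05 × 0.4 = 0.02). At 15% missing overall it moves the LY3209590 mean by 0.15 × 0.4 = 0.06. This is a real check on the noninferiority conclusion. It does not separate on-treatment from off-treatment missing values, correct the primary estimate, or recover lost precision. For superiority, SAP 4.4.1.3 plans only the rerun that includes inadvertently enrolled participants.

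**Conclusion.** The point holds as a gap in the rule that, read literally, mismatches the estimand and can bias the result. A reader might go further and conclude that the US primary analysis is biased. The documents do not support that: with equal missing shares and gaps, retrieved-dropout imputation leaves the treatment difference unbiased, and the fallback distorts it only when there is a true difference or unequal missingness.

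The expected effect is small: a few hundredths of an HbA1c point, against margins of 0.4 and 0.3. It matters most in two settings. At the tighter 0.3 margin, a 0.03 shift costs about 7 points of power (90.1% to 83.3%). Under the fallback, one-sided type I error at the 0.4 margin reaches about 3.1% with 2% missing per arm. All of these sizes rest on assumed missing rates, and the shifts in Step 1 also on an assumed gap. Because the rule governs a primary analysis and is cheap to repair, it should be changed before unblinding.

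**What to change.** In SAP 4.3.2, split the rule by treatment status at Week 52:

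- Missing after discontinuation of study treatment: keep retrieved-dropout imputation, with the existing return-to-baseline fallback.
- Missing while still on study treatment: multiple imputation under missing at random from same-arm participants still on treatment, with baseline HbA1c, earlier HbA1c and rescue use in the imputation model.

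Apply the same split to Week 26 HbA1c, align the Protocol 9.3.2 summary and the SAP 4.1 table with it, and report the number of each type of missing value by arm. The cost is a few sentences and one extra imputation step; sample size and the stated power do not change.

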#### 4.3.3. Sensitivity Analysis

#### 4.3.3.1. Two-way Tipping Point Analysis

To confirm the robustness of the primary endpoint results, a 2-way tipping point analysis represents varying assumptions for missing data from both treatment groups will be conducted. This sensitivity analysis will focus on missing data at the primary endpoint. Penalty parameters for imputed missing values will be added for both treatment arms. The ANCOVA model for treatment regimen estimand will be conducted after penalty parameters are added. The multiple imputation framework by Rubin (1987) will be used to summarize the results. The corresponding p-value of non-inferiority test will be shown by color scale in the figure.

Additionally, imputation under the noninferiority null hypothesis will be conducted by adding 0.4 (NIM) to the imputed data using treatment regimen estimand (Section 4.3.2) for the LY3209590 group only. The ANCOVA model for treatment regimen estimand will rerun using the adjusted data. The multiple imputation framework by Rubin (1987) will be used to summarize the results.

#### 4.3.3.2. Including Inadvertently Enrolled Participants

The primary efficacy analysis will be repeated for both treatment regimen estimand and efficacy estimand by including inadvertent enrolled participants using mITT population.

#### 4.3.3.3. Other Sensitivity Analysis

The following sensitivity analyses will be performed using the same MMRM model as for the efficacy estimand described in Section 4.3.2 based on the EAS2 data.

- Sensitivity analysis will be conducted excluding the data after the change to LY3209590 with a prefilled pen to compare the HbA1c change from baseline to Week 52 (Visit 33) between LY3209590 with the autoinjector and insulin glargine.
- To balance the exposure time for LY3209590 with autoinjector and insulin glargine, sensitivity analysis will be conducted to compare the HbA1c change from baseline to Week 52 (Visit 33) for participants receiving LY3209590 with autoinjector for the whole treatment period and participants receiving insulin glargine.

#### 4.3.4. Supplementary Analyses

Additional analysis may be conducted as needed.

## 4.4. Secondary Endpoint(s) Analysis

#### 4.4.1. Gated Secondary Endpoint

A gatekeeper approach (Westfall and Krishen 2001) will be used to control for type I error for the primary and gated secondary objective. The noninferiority test for the primary objective will be based on the 2-sided 95% CI. Once the upper limit of the 2-sided 95% CI is below the NIM, the non-inferiority is achieved, and the gated secondary objective will be conducted at a 2-sided 0.05 significance level.

#### **4.4.1.1. Definition of Endpoint(s)**

See Section 4.3.1 for the HbA1c change from baseline to Week 52 (Visit 33).

#### 4.4.1.2. Main Analytical Approach

The superiority test in change from baseline to Week 52 (Visit 33) in HbA1c will be based on the same primary endpoint analysis described in Section 4.3.2.

#### 4.4.1.3. Sensitivity Analysis

The analyses described in Section 4.4.1.2 will be repeated for both the treatment regimen estimand and efficacy estimand by including inadvertent enrolled participants using mITT population.

#### 4.4.2. Supportive Secondary Endpoints

#### 4.4.2.1. Other Efficacy Endpoints

The analyses for the other supportive efficacy endpoints of insulin dose, and patient-reported outcomes will be based on the EAS2 data. The analysis of change from baseline for HbA1c at Week 26 and fasting glucose by SMBG at Week 16, 26 and 52 will be performed for both treatment regimen estimand and efficacy estimand.

For treatment regimen estimand, only participants with an observation at baseline or at the endpoint visit will be included in the analysis. The missing baseline will be imputed using multiple imputation under assumption of missing at random. Missing data at the endpoint visit will be imputed using either retrieved dropout or return-to-baseline multiple imputation approach determined by the criterion described for the primary efficacy endpoint in Section 4.3.2. ANCOVA analysis will be conducted similar to that for the primary endpoint. An additional term of baseline HbA1c stratum (<8.0%,  $\ge8.0\%$ ) will be added into the model for the endpoints other than HbA1c.

For efficacy estimand, participants with baseline and at least one post baseline observation will be included in the analysis. The longitudinal observations of actual and change from baseline in HbA1c to Week 26 will be analyzed using the same MMRM model as for the efficacy estimand described in Section 4.3.2. The analyses of other continuous efficacy measures (fasting glucose measured by SMBG) will use an MMRM model similar to that for the primary endpoint with an additional term of baseline HbA1c stratum (<8.0%, ≥8.0%). If a subject does not indicate which BG measurement was fasting, the FBG value will be assigned programmatically by designating the FBG as the first measurement between 5am-10am. These programmatically derived FBG values will also be included in the analysis. The variance-covariance structure in the MMRM models for fasting glucose from SMBG and insulin dose will be based on compound symmetry.

The analysis of study insulin dose will use an MMRM model on the EAS2 data with treatment, strata (country, GLP-1 RA treatment at randomization, and baseline HbA1c stratum [<8.0%, ≥8.0%]), visit, and treatment-by-visit interaction as fixed effects. The average weekly dose during each visit for individual participants will be used in the analysis. In the LY3209590 group, the average dose of each visit (that is, average of weekly doses since last visit) will be used as the average weekly dose. In the insulin glargine group, the average weekly dose will be calculated by the average daily dose multiplying by 7. The analysis will be repeated for average daily dose in U and daily dose in U/kg. The body weight at the visit will be used to calculate the daily dose in U/kg at the same visit.

